7.3 Procedure for Reporting Adverse Events

Adverse event reporting will begin at the time a subject provides written informed consent and ends after a subject withdraws from the study or completes the final study visit.

For screen failure subjects, any AEs, ADEs, and DDs that occur from the time of informed consent up until the date on which the subject is deemed ineligible for the study will be recorded on a case report form.

Only one AE/SAE case report form should be completed per event.

To ensure patient confidentiality, the following reports will include the patient number only.

7.3.1 AE Reporting

In the occurrence of an AE, data should be entered into the AE case report form in the EDC system within five working days of awareness of the event. Safety reporting to the IRB should occur according to the requirements of the local IRB.

7.3.2 SAE Reporting

In the occurrence of a serious adverse event (SAE), expedited reporting requirements are followed. The SAE case report form should be completed in the EDC within 24 hours of awareness of the event. Straumann will receive an automated notification generated by the EDC system.

Safety reporting to the IRB should occur according to the requirements of the local IRB. It is recognized that in many cases SAEs will be treated in a medical rather than a dental environment and the investigator may not have immediate knowledge of the event. The investigator should report an SAE as soon as he/she has knowledge of the event within the above time frame irrespective of when the actual event occurred.

7.3.3 DD Reporting

The Investigator should report all device deficiencies by completing the Device Deficiency CRF.

When a device deficiency leads to a potential AE (e.g. bleeding, pain, swelling, infection, peri-implantitis) the AE case report form in the database needs to be completed in a timely manner.

Moreover, **device deficiencies with SADE potential** (e.g. nerve encroachment, sinus perforation, etc.) must be recorded in the SAE case report form and follow the expedited reporting requirements (**within 24 hours**).

7.3.4 ADE Reporting

Adverse device effects must be recorded and submitted to Straumann by completing the AE case report form in the EDC system within five working days of awareness of the event. Safety reporting to the Institutional Review Board (IRB) should occur according to the requirements of the local IRB.

Bone loss reporting: Continuous substantial reduction of the peri-implant bone level is a sign of failure of the implant system. The first European Workshop on Periodontology specified an average marginal bone loss of less than 1.5 mm bone loss within the first year after the insertion of the prosthesis, and thereafter less than 0.2 mm annual bone loss as criteria for measuring success¹⁸. This has been a standard and a basis for success criteria since it was defined in 1993. In a more recent meta-analysis, the authors looked at Straumann implants and determined that a pooled weighted mean of marginal bone level change for Straumann implants was -0.56 mm (95% CI -0.661, -.481) after 5 years. The individual study means of marginal bone level change ranged from -0.15 to -1.0 mm after 5 years.¹⁹ Based on this information the central radiologist will flag any bone level changes that are greater than 2.5 mm in the first year post-loading and any annual changes greater than 1.5 mm in subsequent years. The study manager will review the flagged values and discuss with the principal investigator whether the bone level change will be reported as an ADE.

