5.2.6 Marginal Bone Level Changes

Bone level changes will be evaluated on a standardized peri-apical radiograph at implant loading and at 12, 24, 36, 48, and 60 months post-loading. The radiographs will be sent to a centralized location to be evaluated in a blinded fashion by a single reader using a calibrated measuring tool. Additional details will be provided in operations manual to describe how the central radiologist will measure the bone level values from the radiographs.

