5.2.8 Implant Success and Survival

Implant survival will be assessed at all visits following the surgical visit. A surviving implant is an implant that is in place at the time of follow-up.

Implant success will be assessed at implant loading, and at 12, 24, 36, 48, and 60 months post loading. A successful implant will meet all of the following criteria according to Buser¹⁶:

- Absence of persistent subjective complaints, such as pain, foreign body sensation, and/ or dysesthesia
- Absence of a recurrent peri-implant infection with suppuration
- Absence of mobility
- Absence of a continuous radiolucency around the implant

[figure not shown]
Non-surviving implants will be counted as an unsuccessful implant.

Any dental implant showing excessive bone loss, radiolucency, or infection shall be treated in the manner best suited to the well-being of the subject, including treatment to save the dental implant. Continuous radiolucency, implant mobility, and recurrent perimplant infection with suppuration shall be recorded on the adverse event form (see section 7.3.4).

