6.12 Visits 10, 11, 12, and 13 - Follow-Up Visits

Subjects will be recalled at 24 months (± 1 month), 36 months (± 1 month), 48 months (± 1 month), and 60 months (± 1 month) post loading. Data from these visits will be used for the additional analyses.

- Periodontal measurements (PPD and mSBI at adjacent teeth)
- Oral hygiene evaluation
- Concomitant mediation
- Adverse event check
- Verbal confirmation of pregnancy status, if applicable
- Standardized periapical radiograph
- CBCT localized

- · Implant survival and success
- Soft tissue evaluation (gingival margin and papilla height)
- Subject satisfaction
- Intra-oral photographs

7 Evaluation of Adverse Events

For the avoidance of doubt, *all* AE/SAEs as defined below, **regardless of whether they are related to the investigational device**, should be collected, fully investigated and documented in the source document and appropriate case report form for all subjects from the time of the signing of the informed consent until the last protocol-specific procedure. Documentation includes dates of event, treatment, outcome, assessment of seriousness and causal relationship to the device and/or study procedure (rationale to be provided).

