7.1.4 Adverse Device Effect (ADE)

An ADE is an adverse event related to the use of an investigational medical device. This definition includes adverse events resulting from insufficient or inadequate instructions for use, deployment, implantation, installation, or operation, or any malfunction of the investigational medical device. This definition includes any event resulting from use error or from intentional misuse of the investigational medical device. Any adverse event which the clinical investigator believes has even a possible relationship to the device will be classified as an ADE.

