10.5 Protocol Amendments

Once the first subject has entered the study, any part of this study plan can be amended upon agreement of the sponsor and the participating principal investigators throughout the

clinical investigation. Protocol changes will be kept to a minimum. Only those changes that are deemed essential to the successful completion of the protocol will be considered.

The reasons and justifications for the amendment will be included with each amended section of the document, and the amendment will include a version number and date. Once the investigator and the sponsor have accepted the changes, a written amendment to the protocol will be sent to the investigator for signature.

All significant protocol changes affecting the scientific soundness of the study or the rights, safety, or welfare of subjects which occur after the initial IRB approval, must be submitted for approval by each center to the IRB as an amendment to the original protocol before the changes can be implemented by the Investigator. Each investigational center will send a copy of the IRB approval letter for the amendment to Straumann.

Requests for clarification statements to the protocol shall be discussed with the study monitor. The clarification statements will be sent to each investigator and will be kept in the appropriate file.

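### Protocol Section 7.3.4 flags bone loss only interval by interval, so slow sustained loss can pass the five-year total implied by its cited criteria without a numeric flag

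*Protocol*

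**What the plan says.** Protocol Section 7.3.4 opens its bone-loss paragraph with the statement that "Continuous substantial reduction of the peri-implant bone level is a sign of failure of the implant system". It then cites two references. One is a consensus criterion: average loss below 1.5 mm in the first year, then below 0.2 mm a year. The other is a meta-analysis with a pooled five-year mean loss of 0.56 mm and individual study means from 0.15 to 1.0 mm. From these it sets the operating rule for the central reading: "flag any bone level changes that are greater than 2.5 mm in the first year post-loading and any annual changes greater than 1.5 mm". The second limit applies to each later year. The study manager reviews flagged values and discusses with the principal investigator whether to report an adverse device effect (ADE).

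Other provisions bear on the same patient:

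- Section 5.2.6: films at loading and at months 12, 24, 36, 48 and 60 are "evaluated in a blinded fashion by a single reader using a calibrated measuring tool".
- Section 5.2.8: "Any dental implant showing excessive bone loss, radiolucency, or infection shall be treated in the manner best suited to the well-being of the subject". No millimeter value defines excessive. The readable success criteria there and in SAP Section 6.1 have no millimeter limit either.
- Section 7 (opening paragraph): all adverse events "should be collected, fully investigated and documented in the source document and appropriate case report form for all subjects".
- Section 7.1.4: "Any adverse event which the clinical investigator believes has even a possible relationship to the device will be classified as an ADE".
- Section 7.2.6: the table of expected ADEs lists peri-implant bone loss, again without a number.
- Section 7.3.4: "Adverse device effects must be recorded and submitted to Straumann by completing the AE case report form".
- SAP Sections 4.3, 5 and 7: change from loading is an endpoint at months 24 to 60, summarized descriptively. The loss categories in Section 5 run up to 3 mm or more.

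**The concern.** The failure sign that the protocol names is sustained loss, but its rule tests each interval separately. That rule is good at catching a sudden drop and poor at catching a slow, steady decline. A patient can lose a moderate amount every year, stay under both limits throughout, and accumulate a total well beyond what the cited criteria allow.

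At stake is the route to review. A flag is what takes a central reading to the study manager and principal investigator. Without one, a slowly progressing patient reaches that discussion only if the site judges the loss to be an adverse event, for which no millimeter threshold is given, or if reading error happens to push one interval over a limit. This is a safety-monitoring gap for individual patients. It does not touch the 12-month comparison or the sample size.

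**Working it through.** **Inputs from the documents.** Flags: above 2.5 mm in year 1 and above 1.5 mm in any later year (Section 7.3.4). Cited criteria: 1.5 mm, then 0.2 mm a year. Cited five-year mean losses: 0.56 mm pooled, 1.0 mm in the worst study. Visit windows: ±1 month (Section 6.1). Subjects who completed month 12: 46 (SAP Section 2.1).

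**Assumptions.** The documents give no reading-error SD and no five-year between-patient SD. I took an SD of a change between two readings, from reading error alone, of 0.25 mm and 0.5 mm. The second value equals the whole SD the protocol assumes for the primary endpoint (Section 8.1), so it leaves no room for biological variation and is an upper bound. The between-patient SD at month 60 was taken as 0.5 to 1.0 mm.

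**Step 1. Totals.**

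- Implied five-year limit: 1.5 + 4 × 0.2 = 2.3 mm.
- Largest total that can escape both flags: 2.5 + 4 × 1.5 = 8.5 mm.

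**Step 2. Steady loss of 0.6 mm a year.**

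| Month | 12 | 24 | 36 | 48 | 60 |
|---|---|---|---|---|---|
| Cumulative loss (mm) | 0.6 | 1.2 | 1.8 | 2.4 | 3.0 |
| Implied limit (mm) | 1.5 | 1.7 | 1.9 | 2.1 | 2.3 |

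The total passes the implied limit at month 48. Each interval change is 0.6 mm, or 0.6 × 14/12 = 0.7 mm at the widest gap between annual visits. Both are below 1.5 mm, so the interval rule is never met by true loss.

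**Step 3. Chance flags.** A later interval is flagged by reading error with probability P(Z > (1.5 − 0.6)/SD).

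- SD 0.25: P(Z > 3.6) = 0.016%. Over four intervals this is about 0.06%.
- SD 0.5: P(Z > 1.8) = 3.6%. Four times this is 14.4%, an approximate upper figure.

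Simulation of 1,000,000 patients, with independent error of SD/√2 on each of the six readings, gives the probability of at least one flag by month 60:

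| Patient | Rule | SD 0.25 | SD 0.5 |
|---|---|---|---|
| 0.6 mm a year | interval (current) | 0.06% | 14.0% |
| 0.6 mm a year | cumulative above 2.5 mm, months 24 to 60 | 97.8% | 86.4% |
| exactly at the cited limits | interval (current) | 0.003% | 4.1% |
| exactly at the cited limits | cumulative above 2.5 mm, months 24 to 60 | 23.6% | 45.4% |

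**Step 4. How many patients.** Expected number above 2.5 mm at month 60 = 46 × P(Z > (2.5 − mean)/SD).

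| Mean (mm) | SD (mm) | z | Probability | Of 46 |
|---|---|---|---|---|
| 0.56 | 0.5 | 3.88 | 0.005% | 0.002 |
| 0.56 | 1.0 | 1.94 | 2.6% | 1.2 |
| 1.0 | 0.5 | 3.00 | 0.13% | 0.06 |
| 1.0 | 1.0 | 1.50 | 6.7% | 3.1 |
| 1.0 | √(1.0² + 0.5²) = 1.12 | 1.34 | 9.0% | 4.1 |

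The last row adds reading error of 0.5 mm.

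**The case against.** **Rarity.** The patients concerned are few. The figure of about 3 needs the worst cited study mean and the widest assumed SD together, and about 4 adds upper-bound reading error. Attrition after month 12 can only lower these counts. This stands, and it is why the point is minor.

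**Other safeguards.** Bone loss is named as an expected ADE. Films, a localized CBCT and an adverse event check occur at every annual visit, and cumulative loss is tabulated. A reader might infer that slow loss would go wholly unnoticed. The documents do not support that: sites have the images and the duty to report. What is missing is narrower, a numeric trigger that sends an individual central reading to review.

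**Extreme cases.** A reader might also picture 1.0 mm a year, 5 mm at month 60 and no interval limit met. The arithmetic is right. But even with the worst cited study mean and an SD of 1.0 mm, the chance of reaching 5 mm is P(Z > 4.0) = 0.003%. The 8.5 mm ceiling shows how loose the rule is and is not a plausible outcome.

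**Looseness of the interval limits.** It is tempting to call 2.5 and 1.5 mm wrong because the cited criteria are 1.5 and 0.2 mm. The cited figures are partly averages, and a flag on one patient's reading must allow for measurement error. The interval limits are therefore not an error in themselves.

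**Unseen material.** The operations manual describes the central reading and is not among the documents, and a figure after the success criteria is not shown. The absence of a cumulative flag is therefore established only for the visible Protocol and SAP. Still, Section 7.3.4 is where the reporting rule is set.

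**Conclusion.** The point holds as a minor gap in safety monitoring. The visible Protocol and SAP contain no flag on cumulative loss from loading, although Section 7.3.4 identifies continuous loss as the sign of failure. True steady loss of 0.6 mm a year ends 0.7 mm above the implied 2.3 mm and would almost never be flagged at the smaller reading error.

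That arithmetic needs only the protocol's own numbers. The flag probabilities and patient counts rest on the assumed SDs, on normal distributions and on independent reading errors. Confidence in their size is moderate. The realistic number affected is about 0 to 1 of 46, and about 3 to 4 at the unfavorable end. Nothing here bears on the primary analysis.

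**What to change.** Keep both interval flags. In Section 7.3.4, add a central-reader flag at the 24-, 36-, 48- and 60-month readings for cumulative loss from loading above 2.5 mm, handled by the same study manager and principal investigator review. The cut-off is a choice: it reuses the year-1 limit and sits just above the implied 2.3 mm. A flag would prompt review and would not make the change an ADE automatically. SAP Section 2.3 lists these visits as still to come, so the change was practicable when the SAP was written.

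No new films or readings are needed, since the flag is one subtraction on existing measurements. The costs are:

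- **Amendment.** It must be agreed by sponsor and investigators. Section 10.5 requires IRB approval at each center for "All significant protocol changes affecting the scientific soundness of the study or the rights, safety, or welfare of subjects", if this change is judged to be one.
- **Extra reviews.** A handful, in line with the counts above.
- **Flags near the limit.** About 24% (change SD 0.25 mm) to 45% (0.5 mm) of patients lying exactly at the cited limits would be flagged at least once. A higher cut-off would reduce this but detect slow loss later.

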7.3.5 SADE Reporting

In the occurrence of a serious adverse device effect, expedited reporting requirements are followed. The SAE case report form should be completed within 24 hours of awareness of the event in the EDC system. Straumann will receive an automated notification generated by the EDC system.

The product safety officer at Straumann will work with the Investigator to determine whether the event is anticipated (ASADE) or unanticipated (USADE). In case of USADE, the investigator must promptly notify its reviewing IRB as soon as possible, but no later than ten (10) working days after first learning of the event.

Since this is a multi-center study, Straumann will inform investigators at all participating centers of any reported USADEs related to this protocol and the study device. Copies of such external USADE reports should be forwarded to the IRB for review and a copy must be kept in the investigator site files.

7.3.6 Additional Safety Reporting

Straumann will report additional safety information to the centers that is relevant to the protocol or study device and may affect the risk/benefit ratio, the rights, safety or welfare of subjects, or the integrity of the study. Such reports may include notification

of any changes to the instructions for use, any publications or interim reports, or any product recalls.

7.4 Monitoring of Subjects with Adverse Events

Any AE that occurs during the course of this study must be monitored and followed-up by the investigator until one or more of the following have occurred:

- The AE is resolved.
- Pathological laboratory findings have returned to normal,
- Steady state has been achieved, or
- It has been shown to be unrelated to the study products.

The outcome of an event will be pursued until resolution or until the last data queries are issued following the subject's last study visit. For screen failure subjects, ongoing AEs, ADEs, and DDs must be followed and updated until the date the subject is deemed a screen failure. For subjects documented as lost to follow-up, ongoing AEs, ADEs, and DDs will not be followed.

It is the responsibility of the sponsor to cooperate with the investigator to assure that any necessary additional therapeutic measures and follow-up procedures are performed.

8 Statistical Analysis Considerations

8.1 Sample Size

The following assumptions were used to determine the sample size for the primary endpoint of mean change in crestal bone level between implant placement and 12 months postimplant loading:

- Subjects will be assigned to either the test or control treatment group
- The primary analysis is a non-inferiority comparison of the test treatment to the control treatment

- The standard deviation for both test and control treatments is 0.5 mm
- A difference between treatment groups of ≥ 0.5 mm is considered clinically significant (i.e., the non-inferiority margin)
- The difference between the treatment groups is expected to be 0 mm
- Greater than 80% power is considered sufficient
- Statistical test will be performed with a one-sided 5% significance level

The hypotheses associated with the primary endpoint are defined as follows:

$$H_0$$
: $\mu_c \ge \mu_s + \delta$

$$H_1$$
: $\mu_c < \mu_s + \delta$

where μ_c is the mean change in crestal bone level for the test implants, μ_s is the mean change in crestal bone level for control implants, and δ is the pre-defined non-inferiority margin of 0.5 mm. The study will be considered successful if the null hypothesis is rejected, i.e., the conclusion of non-inferiority is achieved. If non-inferiority is achieved at a one-sided α of 5%, a one-side superiority test will be performed at significance level of 5%.

To maintain at least 80% power to detect a difference between treatment groups of 0.5 mm with a common standard deviation of 0.5 mm, 14 subjects per treatment group would be required for a total of 28 subjects. Adjusting for potential 25% attrition, 19 subjects per treatment group will be required for a total of 38 subjects. An additional 14 subjects will be enrolled in order to provide more data for the implant success and survival calculations, thereby bringing the total sample size to 52.

8.2 Randomization

The randomization schedule will be generated and held by an independent statistician that will not participate in any other aspect of the study. Subjects will be randomized to either test or control in a 1:1 ratio.

The study randomization schedule will be stratified by study center to ensure that randomization is balanced across the two centers. Further, the randomization will use permuted blocks of appropriate size.

8.3 Analysis Sets

8.3.1 Modified Intention to Treat (mITT) Analysis Set

The analysis of the primary and secondary effectiveness measures will be based on the mITT analysis set. The modified intent to treat analysis set consists of all subjects who are consented in the study, randomized, and received the study device. This analysis set will include subjects regardless of any protocol violations and/or premature termination. This analysis set includes the Per Protocol analysis set.

8.3.2 Intention to Treat (ITT) Analysis Set

The ITT analysis set consists of all subjects who are consented in the study, and randomized (i.e., enrolled). This population will include subjects regardless of any protocol violations and/or premature termination, or whether the subject actually received study treatment, and is based on the subject's randomization assignment rather than actual treatment received. The ITT analysis set will be used for presenting baseline data, procedural information, adverse events and protocol deviations. The ITT analysis set will also be used to provide a sensitivity analysis of the primary effectiveness endpoint. This analysis set includes the mITT population.

8.3.3 Per Protocol (PP) Analysis Set

The PP analysis set consists of all subjects who are consented in the study, randomized, and received the study device according to the study protocol and randomization schedule. Subjects with significant protocol deviations (e.g., deviation of inclusion/exclusion criteria) will be excluded from this analysis set. Subjects with implants that do not reach primary stability will be excluded from this analysis set. Exclusion of subjects based on protocol deviations will be determined on a case-by-case basis with input from the Principle Investigator and study statistician. The determination of which protocol deviations are significant enough to warrant exclusion from PP analysis population will be made while blinded to the subject's randomization assignment and primary endpoint result, and prior to final analysis. The PP analysis set will be used to provide a sensitivity analysis of the primary effectiveness endpoint.

The results based on the ITT and PP analysis sets are intended only to assess the robustness of the primary findings based on the mITT population.

